5.7 Subject Withdrawal

Participants may choose to withdraw from the study at any time. They do this by providing verbal or written communication to this effect. Withdrawal from the study will not impact employment status within the cancer center. The Principal Investigator may withdraw subjects who violate the study plan, to protect the subject for reasons related to safety or for administrative reasons. Whether or not each subject completes the study will be tracked.

5.8 Timeline

Over 2 years, our multi-disciplinary team will plan, implement, and evaluate, the project. **Aims 1-2** of the project will be accomplished by organizing tasks into four main areas. Planning, which is already fully underway, involves assembly and training of the multi-disciplinary team, refinement of key project elements, recruiting clinician participants, and modification of the CDS logic. Given our ongoing planning, we expect needing only 3 months before moving into the next phase. Implementation involves program initiation, roll-out of the TUT Service+VM CDS protocol, and preparation of evaluation tools. We expect to have the CDS fully operational by month 7. Evaluation will start within one calendar quarter of implementation, and will run for the duration of the project.

Months/Task	1	2	3	4	5	6	7	8	9	10	11	12	13	14	15	thru	24
Plan																	
Implement																	
Evaluate																	
Sustain																	

6 Statistical Plan

All data will be maintained on password-protected computers within a DMS that uses ORACLE and MS ACCESS to permit web-based real-time data entry, storage, and QA.

6.1 Sample Size and Power Determination

Engagement rates are our primary measure of effect. Given that our initial educational intervention was able to change absolute engagement rates by approximately 20%, we assume that a CDS intervention would need to accomplish an equivalent amount of change to be clinically relevant. There are over 1000 BPA activations annually, resulting in approximately 600 TUT Service referrals per year (Engagement rate ~ 60%). To detect improvement in Engagement rate to 80%, with 80% power and a significance level of $p=0.05$, we need to enroll 24 clinicians to each arm. Retention: Because of project nature, we assume drop-out will be minimal (<10%) after enrollment; 26 subjects per arm ensures power.

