2.1 Primary Objectives

The objective of this study is to examine a novel approach to improving the quality of care inpatients receive if they use tobacco (oncology and general inpatients).

Specific Aim 1: *Assess whether including a standing order for prescription and management of varenicline (TUT Service+VM) within the inpatient clinical workflow for cancer and non-cancer patients identified as current smokers will significantly increase TUT engagement rates compared to current standard of care (TUT Service alone). Hypothesis:* Observed treatment engagement rates will be higher among clinicians exposed to TUT Service+VM than observed in clinicians exposed to TUT Service alone.

Specific Aim 2: *Assess whether clinicians exposed to the TUT Service+VM condition will be more effective at guiding reluctant patients toward TUT engagement than clinicians exposed to the TUT Service alone condition. Hypothesis:* Rates of important TUT behaviors (e.g. treatment initiation, quit attempts, and others) observed among smoking patients of clinicians exposed to TUT Service+VM will be higher than those than observed among smoking patients of clinicians exposed to TUT Service alone.

Specific Aim 3: *Assess implementation preferences and barriers influencing effectiveness of usual care tobacco use treatment (TUT Service) + varenicline management (VM) applied within the cancer center. Hypothesis:* Oncology specialists exposed to the TUT Service + VM condition will identify key facilitators and barriers to the implementation of the TUT Service + VM condition that can help guide subsequent dissemination efforts.

The goal of this study is to determine if the default for a varenicline order increases clinician referral to TUTS and/or the treatment of tobacco use. At this point, many clinicians are turning the referral order off and patients are not receiving treatment for tobacco use. A default to prescribe treatment may help override barriers to both. While we are focused on cancer inpatients, we will assess the impact of the varenicline management intervention on cancer and non-cancer patients.

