4.1 General Design

To achieve all of our research objectives, we plan to conduct a two-arm RCT pilot study of a CDS intervention, exposing half of our clinician sample to the TUT Service+VM condition during clinical workflow and comparing important outcome measures to those observed among the half exposed to the current usual care condition, TUT Service alone. Following the conclusion of the pilot study, clinicians will be surveyed about implementation preferences and barriers influencing effectiveness of the intervention.

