4.2 Study Measures

Our current usual care CDS “fires” a Best Practice Alert (BPA) for each new inpatient within the Medical Assistant (MA) check-in and vital sign workflow. The BPA requires that MAs assess tobacco use status within the past 30 days and satisfy the alert with one of three possible, mutually exclusive answers.

Intervention ordering rate is defined as the number of patients for whom any inpatient tobacco use treatment order (for medication, education, and/or TUTS counseling) was signed divided by the total number of patients in each arm for whom an order was pended and the alert fired. MAs activate “Order” tab for all patients identified as current smokers (within 30 days), resulting in placement of pended order for consult to TUT Service referral within clinical workflow.

Inpatient medication ordering rate is defined as the number of patients for whom a tobacco use treatment medication was ordered in the inpatient setting divided by the total number of patients in each arm for whom an order was pended and the alert fired.

Outpatient/discharge medication ordering rate is defined as the number of patients for whom a tobacco use treatment medication was ordered upon patient discharge from the hospital divided by the total number of patients in each arm for whom an order was pended and the alert fired.

TUTS referral rate is defined as the number of patients for whom a referral to Penn Medicine’s Smoking Cessation Program was placed in the inpatient setting divided by the total number of patients in each arm for whom an order was pended and the alert fired.

These measures will be collected only from patients referred to [name] program for treatment:

Quit Line rate, defined as the total number of patients who present for quit line counseling (i.e. telephone or electronic), divided by the total number of patients referred to the Smoking Cessation Program

Medication recommendation rate, defined as the total number of patients who are recommended to receive a tobacco use treatment medication by the TUT Service staff in quit line counseling divided by the total number of patients who present for quit line counseling

Follow-up recommendation rate, defined as the total number of patients who are recommended to receive a tobacco use treatment medication or a follow-up appointment by the TUT Service staff in quit line counseling divided by the total number of patients who present for quit line counseling

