5.4 Inclusion of Non-cancer Patients

After testing the logic of the usual care intervention and the Novel BE intervention, it was determined that these two groups were being treated differently. In the usual care intervention, clinicians would receive the standard TUT Service BPA for all patients, regardless of cancer status. However, in the Novel BE intervention, the clinicians would receive the TUTS + VM BPA for their patients with a cancer history but would also be exposed to the standard TUT Service BPA for their patients without a cancer history. To ensure that these two groups are experiencing the same treatment, we are altering the study logic so that the clinicians randomized to the study Novel BE intervention will be exposed to the TUTS + VM BPA regardless of a patient's cancer status. This will also allow us to test the effect of the intervention on all inpatients, on non-cancer in-patients, and on just cancer inpatients. This change simplifies the system and expands our ability to test the impact of the intervention on differing in-patient populations.

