6.2 Statistical Methods

For Aims 1 and 2, rate comparisons between the two groups will be performed using Chi-square. We will examine the impact of the intervention on tobacco treatment rates across cancer inpatients, non-cancer in-patients, and all in-patients.

7 Safety and Adverse Events

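### The 24 clinicians per arm in Section 6.1 do not follow from the stated inputs, which give 82 patients or alerts per arm, and the unadjusted chi-square in Section 6.2 does not fit randomization by clinician

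*Combined protocol and SAP*

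**What the plan says.** Section 6.1 makes engagement rate the primary measure and takes its baseline from alert counts: "There are over 1000 BPA activations annually, resulting in approximately 600 TUT Service referrals per year (Engagement rate ~ 60" percent. To detect a rise to 80% with 80% power at p=0.05 it states that "we need to enroll 24 clinicians to each arm". After allowing for drop-out below 10% it concludes that "26 subjects per arm ensures power". It names no formula, sidedness, number of alerts per clinician, ICC or between-clinician SD.

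Clinicians are the units assigned to arms. Section 4.1 describes "exposing half of our clinician sample to the TUT Service+VM condition", and Section 5.4 says that "clinicians randomized to the study Novel BE intervention will be exposed to the TUTS + VM BPA". The ordering and referral rates in Section 4.2 are counted over patients: each is "divided by the total number of patients in each arm for whom an order was pended and the alert fired". No measure in Section 4.2 is called engagement rate. The Aim 1 hypothesis in Section 2.1 speaks of clinicians: "Observed treatment engagement rates will be higher among clinicians exposed to TUT Service+VM".

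For Aims 1 and 2, Section 6.2 says only that "rate comparisons between the two groups will be performed using Chi-square". The synopsis says the same. Neither mentions clustering or a clinician-level summary.

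**The concern.** The stated inputs are a comparison of two proportions, and the stated result is a number of clinicians. The step between them is missing. The baseline rate is per alert, the measures are per patient and the randomization is per clinician, so a reader cannot tell what the 24 counts or check it.

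Two things are at stake. First, the 52-clinician target and the assurance of power both rest on this derivation. Second, the test in Section 6.2 cannot carry a clinician-based power statement. Applied to pooled patient counts, it treats patients of the same clinician as independent. The Introduction reports marked differences between clinicians in engagement and uses them to motivate the study, so an ICC of zero cannot be presumed. With a positive ICC the chi-square gives confidence intervals that are too narrow and too many false positives. Section 9.4 intends the results to support a later large trial, so a false positive could carry forward.

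**Working it through.** **1. The plan's own figure.** Inputs from Section 6.1: p1 = 0.60, p2 = 0.80, mean 0.70, difference 0.20, alpha 0.05, power 80%. The pooled two-sided formula is

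n = [1.960·√(2·0.70·0.30) + 0.842·√(0.60·0.40 + 0.80·0.20)]² / 0.20² = 81.2, so 82 per arm.

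| Variant | Two-sided | One-sided |
|---|---|---|
| Pooled | 82 | 64 |
| Continuity-corrected | 91 | 74 |
| Unpooled | 79 | 62 |
| Arcsine | 81 | 64 |

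None is near 24. If each clinician supplied one binary result, two-sided power would be 32% with 24 per arm and 35% with 26. The step from 24 to 26 is not the problem: 24/0.9 = 26.7, and 24 clinicians remain if drop-out is at most 2/26 = 7.7%.

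**2. What would give 24.** A two-sided t-test on clinician rates with 24 per arm has 80% power at a standardized difference of 0.826, which implies an SD of 0.20/0.826 = 0.242. A clustered calculation with 4 alerts per clinician and ICC 0.05 also gives 24, as 82·(1 + 3·0.05)/4 = 23.6. Each route needs an input that the plan does not state.

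**3. Cluster-adjusted power.** Let K be clinicians per arm and m alerts per clinician. The effective number per arm is K·m / [1 + (m − 1)·ICC], put into the pooled two-sided formula with equal cluster sizes. Unequal alert counts would lower power.

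Every m and ICC here is an assumption. Section 6.1 gives over 1000 alerts a year and Section 3.1 gives 18 months of data, hence about 1500 alerts. Section 3 speaks of a pool of several hundred clinicians. Spreading 1500 alerts over 400, 200 or 52 clinicians gives m = 3.75, 7.5 or 28.8. The annual count is not tied to a site, to cancer status or to the 52 clinicians, so the true m may lie outside this range.

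Each cell lists results for ICC 0.05 / 0.10 / 0.20 / 0.30.

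| m | Power, K = 24 (%) | Power, K = 26 (%) | Detectable difference from 60%, K = 24 (points) |
|---|---|---|---|
| 3.75 | 79 / 74 / 66 / 58 | 82 / 78 / 69 / 62 | 20.2 / 21.3 / 23.2 / 24.9 |
| 7.5 | 95 / 90 / 79 / 68 | 97 / 92 / 82 / 71 | 15.8 / 17.5 / 20.3 / 22.7 |
| 28.8 | >99 / 99 / 89 / 76 | >99 / 99 / 92 / 79.5 | 11.0 / 13.7 / 17.8 / 20.9 |

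Power reaches 80% in 5 of 12 scenarios with 24 per arm and in 7 of 12 with 26. The largest ICC that keeps 80% with 24 per arm is 0.039, 0.187 and 0.270 for the three values of m.

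**4. Type I error of the planned test.** With design effect DE = 1 + (m − 1)·ICC, the true two-sided error of an unadjusted chi-square at nominal 5% is 2·[1 − Φ(1.96/√DE)].

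| m | DE, ICC 0.05 to 0.30 | Type I error, ICC 0.05 / 0.10 / 0.20 / 0.30 (%) |
|---|---|---|
| 3.75 | 1.14 to 1.82 | 7 / 8 / 12 / 15 |
| 7.5 | 1.32 to 2.95 | 9 / 13 / 20 / 25 |
| 28.8 | 2.39 to 9.35 | 20 / 31 / 44 / 52 |

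A beta-binomial simulation (20,000 runs, 24 clinicians per arm, 60% in both arms, m = 4, 8 and 29) gave chi-square error of 6.3–15.6%, 9.4–26.4% and 20.6–52.5%. A t-test on clinician rates held 4.8–5.3%.

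**The case against.** The best defence is that 24 is undocumented but not shown to be wrong. The Aim 1 hypothesis refers to clinicians, clinicians are randomized, and an SD near 0.24 is a plausible spread of clinician rates. That stands: 24 may come from a sound clinician-level calculation. But that calculation is not in the plan, and the pooled-rate chi-square in Section 6.2 would not be its matching test.

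The low end of the power range can also be challenged. It spreads alerts evenly over 400 clinicians, whereas Section 3.3 requires a patient with tobacco use disorder in the 30 days before recruitment, and the annual count is a lower bound. If that month were typical (an assumption), m would be about 18 over 18 months. Power with 24 per arm would then be 99.8 / 98 / 87 / 74% at the four ICC values. This is a fair reason to read the m = 3.75 row as an extreme. The same m makes the chi-square worse, with type I error from 15% to 43%.

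It is also true that inflation above 5% follows automatically from any positive ICC with m above 1, and that the 52% figure pairs the largest m with the largest ICC. The direction is firm; the size depends on the assumptions. Calling the study a pilot does not remove the point, because Aim 1 is a hypothesis test and Section 6.1 makes an explicit power claim.

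**Conclusion.** The concern holds. The inputs in Section 6.1 give 82 patients or alerts per arm (64 if one-sided), no standard two-proportion formula gives 24, and the conversion to clinicians is not stated. The claim that 26 per arm secures the power is therefore unsupported. It is not shown to be false: whether power reaches 80% depends on alerts per clinician and on the ICC, neither of which the documents supply.

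The firmer fault is the mismatch between design and test. With clinicians randomized and known to differ, an unadjusted chi-square on patients does not hold its 5% level, and the excess grows with the number of alerts per clinician. This should be corrected before analysis. It gives no reason to change recruitment.

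**What to change.** Keep 52 clinicians.

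- **Section 6.1:** define the engagement rate and its unit, and state the sidedness, the expected alerts per clinician over the data-collection period, and an ICC. Take the ICC from usual-care alert data if these exist by clinician; otherwise use an assumed range. Replace the present claim with the power, or the detectable difference, for 24 to 26 clinicians per arm, given as a range. If 24 came from a clinician-level t-test, state the SD and its independent source. The value 0.24 must not be back-solved from 24.
- **Section 6.2:** replace the unadjusted chi-square with a comparison of clinician-level rates or a cluster-adjusted patient-level analysis, so that the test and the power statement match.

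The cost is two rewritten paragraphs and slightly more analysis, with no change to recruitment or conduct. Trial alerts must stay linked to the clinician. Section 8.1 already gives each clinician a unique study number, but Section 5.5 does not say that the quarterly reports are broken down by clinician, so the planning ICC may have to be assumed. The stated power may look less favourable, and the adjusted confidence intervals will be wider than unadjusted ones.

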6.2 Statistical Methods

For Aims 1 and 2, rate comparisons between the two groups will be performed using Chi-square. We will examine the impact of the intervention on tobacco treatment rates across cancer inpatients, non-cancer in-patients, and all in-patients.

7 Safety and Adverse Events

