significantly improved rates of TUT within oncology practice, however we have identified a number of important social-motivational obstacles to reaching our target of universal TUT. For instance, we know that simple changes to treatment choice architecture in the electronic health record (EHR), i.e. utilizing an “opt-out” rather than “opt-in” structure, increases TUT Service engagement in a manner similar to other contexts of cancer care.(9) Unfortunately, there remains unacceptable variation in clinician engagement rates. One significant reason for this variation is the individual clinician’s perceptions of treatment effectiveness.(10–12) A strategy used elsewhere involved utilizing opt-out orders aimed at maximizing the use of varenicline, i.e. “Varenicline Management” (VM). VM resulted in increased clinician utilization and patient cessation within a relatively controlled environment of hospital-based cardiac and pulmonary care.(13,14) However, it is unknown whether this type of intervention is generalizable to the complex, challenging environment of inpatient oncology.

Our research objective is to identify a simple, pragmatic, innovative way of enhancing TUT rates within inpatient medical care and, specifically, for oncology inpatients. To investigate this possibility, we propose methods that will allow us to: 1) evaluate the impact of standing orders to initiate a varenicline management protocol within inpatient medical treatment workflow (that will include cancer and non-cancer patients) and 2) assess the potential for an EHR-based intervention to affect patient TUT behaviors.

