5.5 Data Collection

All clinicians and sites use EpicCare (Epic Systems Corporation, Verona, WI) to deliver care. Penn Medicine Information Systems (IS) - [name], Penn EPIC Research Team - oversees successful integration of TUT Service CDS into ACC workflow. [name] generates quarterly reports and delivers them electronically to the TUT Service managers ([name], and [name]). Aim 1 & 2 data is of high quality; each report is assessed for quality and accuracy through review of the primary medical record in a random subset of instances. Aim 2 utilizes self-reported measures of effect, derived from in-person clinical (CTTS) contact, providing multiple opportunities to confirm the accuracy of self-reported status. Our experience to date suggests that these measures are highly reliable global metrics. To protect subject privacy, clinician decision-making and patient health record security is stronger than with most other web-based utilities. Numerous layers of data security ensure confidentiality. Data Transfer is exclusively via SSL encryption, protecting data transfer between staff. This is the same technology that is used to protect consumer information (e.g., credit cards) from interception in transit over the Internet. All research data is stored in a secure Oracle database housed behind secure health system firewall.

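### The Aim 1 comparison makes no use of each clinician's pre-launch order or referral rate, leaving avoidable variance (not bias) in a trial of 26 clinicians per arm

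*Combined protocol and SAP*

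**What the plan says.** Section 6.2 gives one method for Aims 1 and 2: "rate comparisons between the two groups will be performed using Chi-square". The synopsis repeats it. The only refinement is a breakdown by cancer status. No section mentions a pre-trial clinician rate, a covariate, or stratified or matched allocation.

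Allocation is by clinician: Section 4.1 describes "exposing half of our clinician sample to the TUT Service+VM condition during clinical workflow". The ordering and referral rates in Section 4.2 pool patients, each being "divided by the total number of patients in each arm for whom an order was pended and the alert fired".

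Three places bear on whether a baseline rate exists and matters:

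- The Introduction says that "there remains unacceptable variation in clinician engagement rates", and Section 2.1 adds that many clinicians switch the referral order off.
- Section 4.2 describes the usual-care alert as current practice for new inpatients, and Section 3 says the referral order is already in the EHR. Section 6.1 counts over 1000 alert activations and about 600 referrals a year.
- Section 5.5 says the EHR research team "generates quarterly reports and delivers them electronically to the TUT Service managers".

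**The concern.** The trial rests on the premise that clinicians differ in how readily they act on the alert. With 26 clinicians per arm, simple allocation can place noticeably more high-referring clinicians in one arm. Neither the design nor the analysis does anything about this. A clinician's own past rate is a natural covariate for the later rate, and it can be measured before launch. At stake is the width of the confidence interval around the Aim 1 effect, and how far a reader can trust that an observed difference is not partly an unlucky draw.

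**Working it through.** **The plan's own figure.** Section 6.1 sets out the target "To detect improvement in Engagement rate to 80%, with 80% power", from 60%, at a 0.05 level, and arrives at 24 clinicians per arm (26 with drop-out).

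- Two independent proportions, two-sided: n = [1.96·√(2·0.7·0.3) + 0.842·√(0.24 + 0.16)]² / 0.2² = 3.25/0.04, which rounds up to 82 per arm, not 24.
- Means of clinician rates: n = 2·(1.96 + 0.842)²·SD²/0.2² gives 24 if SD ≈ 0.245, a value the plan does not state.

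The failure to reproduce 24 is a separate matter, and nothing below depends on it.

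**Inputs.** From the documents: control rate 60% (variance 0.6·0.4 = 0.24), target difference 20 points, 26 clinicians per arm, over 1000 alerts a year, 18 months of data, a pool of several hundred clinicians. Assumed, because the documents are silent: ICC 0.05 to 0.20; share of between-clinician variance explained by the baseline 25% to 49% (correlation 0.5 to 0.7 with the clinician's true follow-up rate); alerts per clinician.

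Alerts per clinician depend on who generates the 1000. If all fell on the 52 participants, that is 1000/52 ≈ 19 a year and 1500/52 ≈ 29 over 18 months. Spread over several hundred clinicians, it is about 3 to 5 a year, so up to about 8 over 18 months.

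**Step 1: chance imbalance in true baseline rates.** SD between clinicians = √(ICC·0.24); SE of the arm difference = SD·√(2/26).

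| ICC | SD | SE of difference | 95% range |
|---|---|---|---|
| 0.05 | 0.110 | 0.030 | ±6.0 points |
| 0.10 | 0.155 | 0.043 | ±8.4 points |
| 0.20 | 0.219 | 0.061 | ±11.9 points |

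**Step 2: gain from adjustment.** With m follow-up alerts, the variance of one clinician's observed rate is ICC·0.24 + (1 − ICC)·0.24/m. Adjustment acts only on the first term. If B is the between-clinician share of the total and R the fraction of it explained, the standard error is multiplied by √(1 − R·B).

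| ICC | m | B | Unadjusted SE (points) | Adjusted SE, R = 25% / 49% | Reduction |
|---|---|---|---|---|---|
| 0.05 | 8 | 30% | 5.6 | 5.4 / 5.2 | 4% to 8% |
| 0.05 | 29 | 60% | 3.9 | 3.6 / 3.3 | 8% to 16% |
| 0.20 | 8 | 67% | 7.4 | 6.8 / 6.1 | 9% to 18% |
| 0.20 | 29 | 88% | 6.5 | 5.7 / 4.9 | 12% to 25% |

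Example, row 1: 0.012 + 0.228/8 = 0.0405; B = 0.012/0.0405 = 30%; SE = √(2·0.0405/26) = 0.056; 1 − √(1 − 0.25·0.296) = 4%.

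**Step 3: sparse baseline.** With 4 baseline and 8 follow-up alerts and perfectly stable habits, the correlation of observed rates cannot exceed 0.012/√(0.069·0.0405) = 0.23 at ICC 0.05, or 0.048/√(0.096·0.072) = 0.58 at ICC 0.20. The standard error then falls by 1 − √(1 − 0.23²) ≈ 3% to 1 − √(1 − 0.58²) ≈ 18%. If true rates before and after correlate at only 0.7, these become about 1% and 9%.

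**Step 4: bias.** In a simulation under no effect (4000 runs per setting, SD 0.10 to 0.25), the mean estimate was within 0.3 points of zero both with and without adjustment.

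**The case against.** The strongest reply is that nothing here is an error. Under randomisation the unadjusted difference is unbiased, a correct clinician-level standard error already allows for chance imbalance, and this is described as a pilot. That stands: the point concerns efficiency.

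The documentary basis for the covariate is also thinner than it looks. A reader might infer that the alert system already reports each clinician's rate. The documents do not say so: the 1000 and 600 are aggregate counts not tied to the 52 participants, and the quarterly reports are described in connection with cancer-centre workflow. The remark on variation between clinicians concerns oncology practice, whereas the trial enrols Department of Medicine hospitalists and attendings. Extraction remains a sound inference, because each alert and order is an EHR event and Section 10.1 plans to identify clinicians and their patients through the EMR.

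A reader might also take a 25% to 49% cut in between-clinician variance as the cut in total variance, which would put the standard error 13% to 29% lower. That would require no patient-level binomial variance, which adjustment does not remove. Step 2 gives the right range.

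Finally, eligibility guarantees only one patient with tobacco use disorder in the 30 days before recruitment, so some baseline rates will be very noisy. This limits the gain but does not remove the case for the covariate.

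**Conclusion.** The point holds as a precision issue. Section 6.2 omits a prognostic covariate that very likely can be obtained, in a trial with few randomised units. At an assumed ICC of 0.05 to 0.20, chance imbalance spans about ±6 to ±12 points against a 20-point target. The standard error would fall by about 4% to 25%, depending on ICC, alerts per clinician and the strength of the baseline. With few baseline alerts and changing habits the gain could be as little as 1%. None of the deciding inputs is in the documents, so these are ranges, not estimates.

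It would be wrong to conclude that the unadjusted comparison is biased; the simulation in Step 4 shows no such effect. The patient-level Chi-square has a more serious and separate fault: it ignores clustering by clinician. In the same simulation it rejected a true null in 8% to 25% of runs with 8 follow-up alerts per clinician and 19% to 51% with 29, against about 5% for clinician-level analyses. A baseline covariate alone would not cure that.

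**What to change.** In Section 6.2, pre-specify for Aim 1 one primary model: either a clinician-level weighted regression, or a mixed logistic or GEE model with clinician as the cluster. Include the clinician's pre-launch rate as a covariate.

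- Define the pre-launch rate with the same numerator and denominator as the Aim 1 outcome, over a fixed look-back of 12 months or longer that ends before the recruitment e-mail in Section 3.5.
- Shrink each rate toward its service-line mean, using pre-launch data only. Clinicians with few or no prior alerts then stay in the analysis without a special rule.
- Fix this wording before any outcome data are compared by arm, since a covariate chosen afterwards would not be credible.

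The clinician-level or mixed model also deals with the clustering fault.

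The change is cheap but not free. It needs one retrospective EHR extract beyond the planned 18 months of data, a check that the consent and HIPAA waiver requested in Section 10.2 covers that extract, and one degree of freedom among 52 clinicians. It needs no new patients or procedures.
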